## **9. Monitoring**

### **9.1 Data Quality**

Quality control procedures for this data include routine (i.e., quarterly) monitoring by the Principal Investigator of:

1. the removal of direct identifiers from information contained with the EHR data and Qualtrics data;
2. the documentation of investigator access to the Qualtrics;
3. any conditions that may negatively impact the confidentiality of information contained within the research registry.

### **9.2 OHSU Knight Cancer Institute Data & Safety Monitoring Plan**

This study is under the oversight of the Knight Cancer Institute’s Data and Safety Monitoring Committee (DSMC) as described in the Knight institutional Data & Safety Monitoring Plan (DSMP). The Knight DSMP outlines the elements required to ensure the safety of clinical study participants, the accuracy and integrity of the data and the appropriate modification of cancer-related clinical research for which significant benefits or risks have been discovered or when the clinical study cannot be successfully concluded. The Knight DSMP also describes the methods and procedures for ensuring adequate oversight of cancer-related research at OHSU.

As described in the Knight DSMP, regardless of a study’s risk level and any specific Knight oversight in place, the Investigator is singularly responsible for overseeing every aspect of the design, conduct, and final analysis of his/her investigation. The DSMC is responsible for conducting Quality Assurance audits on CI approved protocols. This low risk investigator-initiated study may be randomly audited by the

DSMC audit team.

## 10) Risks and Benefits

### a. Risks to Subjects

The primary risk to subjects is related to the small possibility of disclosure of legally protected personal health information (PHI) via EHR data acquisition or qualitative data collection (i.e., interviews). This potential risk will be described in the Information Sheet. Identities of interviewees will not be disclosed in study documents.

### b. Potential Benefits to Subjects

Clinicians exposed to the intervention may gain additional knowledge and expertise for diagnosing and managing skin cancers. Practice members who attend the group training in person will receive a lunch and participating clinics may receive at least 1 SKLIP dermoscopy device for every 2 clinicians in the intervention clinics. SKLIP devices may be kept by clinics at the conclusion of the intervention.

Participants who are invited and complete a one time interview will receive \$100 dollar Amazon gift card.

### c. Ethical and Regulatory Requirements

#### a. Protocol Review

The protocol and informed consent form for this study must be reviewed and approved in writing by the OHSU Knight Cancer Institute (Knight) Clinical Research Review Committee (CRRC) and appropriate Institutional Review Board (IRB) prior to any patient being registered on this study.

#### b. Changes to Protocol

Any modification of this protocol must be documented in the form of a protocol revision or amendment signed by the principal investigator and approved by the CRRC and IRB, before the revision or amendment may be implemented. The only circumstance in which the amendment may be initiated without regulatory approval is for a change necessary to eliminate an apparent and immediate hazard to the patient. In that event, the investigator must notify the CRRC and IRB in writing within 5 working days after the implementation.

#### c. Privacy, Confidentiality, and Data Security

Study staff will be trained to handle data securely for this study. Only staff members who have completed OHSU's required CITI and IRB trainings will be allowed to conduct study activities. The study PI, [name] will be responsible for ensuring that all individuals have satisfied this requirement and will monitor completion of any renewals or additional trainings over the course of the study.

EHR Data: Our protocol and procedures for using EHR data ensures no patients are individually identifiable for analyses. Data will be destroyed three years after completion of all study activities.

Training observations: fieldnotes from observations will be de-identified prior to analysis and saved at OHSU on secure, password-protected servers, including the X drive, Sharepoint or OneDrive. Research staff have training and expertise in high-quality data management and project operations.

Interview data: To minimize risks related to qualitative data analysis, any identifying information will be removed during transcription and signed informed consent will not be obtained. The audio (or video) files from interviews will be destroyed once transcribed. The interviews contain no questions about PHI, though prior to the interview participants' name, email, and phone number may be collected. Access to data will be restricted and require OHSU ID/password authentication. Transcribed data will be destroyed after three years of completion of all study related activities. All files will be stored on the OHSU approved cloud storage software and behind a password and OHSU firewall. Data will be destroyed three years after completion of all study activities.

**d. Maintenance of Records**

If the investigator relocates or for any reason withdraws from the study, the study records must be transferred to an agreed upon designee, such as another institution, another investigator, or to OHSU Knight Cancer Institute Clinical Research Management. Records must be maintained according to sponsor or FDA requirements. State requirements specific to this protocol.

**e. Inclusion of Women, Minorities and Children**

No OHSU Knight Cancer Institute study will focus on any particular gender, racial or ethnic subset. No subject will be excluded from the study on the basis of gender, racial or ethnic origin. Male, female and minority volunteers will be recruited for this study from the general population and approximately 50% men and 50% women will be studied.

The projected gender, racial and ethnic composition of the study will represent that of the Oregon population of patients seen in one OHSU Family Medicine rural-based clinic and one urban underserved Federally Qualified Health Center (FQHC) clinic.

**Table 2: Projected Accrual for the Present Study - Estimated using total unique patients seen in an Oregon Family Medicine rural-based clinic from 1/1/21-12/31/21 time frame**

Ethnic Category	Sex/Gender			
	Females	Males	Unknown	Total
Hispanic or Latino	331	209		4.9
Not Hispanic or Latino	5092	3898		81.8
Unknown	828	630		13.3
Ethnic Category: Total of all subjects*	6251	4737		100.0
Racial Category				
American Indian or Alaskan Native	75	57		1.2
Asian	90	35		1.1
Black or African American	36	39		0.7
Native Hawaiian or other Pacific Islander	19	10		0.3
White	4994	3853		80.5

Ethnic Category	Sex/Gender			
	Females	Males	Unknown	Total
More than one race	212	132		3.1
Unknown	825	611		13.1
Racial Category: Total of all subjects*	6251	4737		100*

**Table 3: Projected Accrual for the Present Study - Estimated using total unique patients seen in an Oregon Family Medicine urban underserved FQHC from 1/1/21-12/31/21 time frame**

Ethnic Category	Sex/Gender			
	Females	Males	Unknown	Total
Hispanic or Latino	561	437		8.5
Not Hispanic or Latino	5367	3678		80.0
Unknown	842	897		11.5
Ethnic Category: Total of all subjects*	6670	5012		100.0
Racial Category				
American Indian or Alaskan Native	94	47		1.2
Asian	321	242		4.8
Black or African American	417	302		6.2
Native Hawaiian or other Pacific Islander	38	22		0.5
White	4700	3579		70.9
More than one race	340	229		4.9
Unknown	760	591		11.6
Racial Category: Total of all subjects*	6670	5012		100*

**Source:** Adapted from U.S. Census Bureau, 2010 \*Totals may not equal 100 due to rounding.

Enhancing Skin Cancer Early Detection and Treatment in Primary Care

NCT05675709

March 1, 2025

Final approach to analysis

Analyses

We used descriptive analyses to examine participating clinician characteristics and rates of e-consults, dermatology referrals and biopsies performed (defined as the number of cases per 1000 patients). We conducted a paired t-test to evaluate change in knowledge scores and used generalized estimating equation-based (GEE) models with link function of Poisson distribution and an exchangeable correlation structure to compare referral outcomes. The models included exposure to training (Yes/No), pre- and post-training time periods and the interaction of these two indicators as predictors. All analyses were two-sided, statistical significance was set at type I error of 5% and analyses were conducted using R Statistical Software.

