## 2) Objectives

This mixed method study will evaluate whether a multicomponent education strategy improves the ability of Primary Care Providers (PCPs) to identify and triage skin cancer. This study will be deployed in two OHSU family medicine clinics: one OHSU Family medicine rural-based clinic and one urban underserved Federally Qualified Health Center (FQHC) clinic. Baseline data and those not participating in the training will serve as controls.

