## 4) Study Design

This study is a mixed method pilot study to determine whether multicomponent education module improves the ability of Primary Care Providers (PCPs) to identify and triage skin cancer. The main independent variable is the multicomponent education for clinicians. This is primarily a feasibility study to evaluate the engagement and uptake of the training and change in skin cancer screening behavior on the part of clinical teams. We hypothesize that exposure to the intervention will increase clinician knowledge, increase the use of a SKLIP dermoscopy device to facilitate capture of high-resolution dermoscopy images, and increase screening for skin cancer.

Outcomes:

- Uptake of the training and performance of skin cancer screening processes measured by proportion of clinicians invited to participate in the educational intervention that complete the training modules; use of the Epic smart tool and dotphrases.
- Clinical knowledge measured through pre- and post-tests implemented during live (in-person or virtual) training.
- Use of the risk assessment tool measured through EHR data.
- Identification of suspicious lesions measured through EHR data.

We hypothesize that the multicomponent education strategy will result in the diagnosis of more skin cancers at earlier stages. Primary endpoints of the study include the pre- and post-intervention: number of melanomas biopsied, mean and median Breslow depth of melanomas biopsied, number of other malignant skin tumors biopsied, total number of referrals to dermatology, number of referrals to dermatology for concerning moles, and number of OHSU PCPs who access the Melanoma Toolkit for Early Detection (MTED), an online Continuing Medical Education training. There will be two comparison groups: OHSU PCPs receiving the intervention, OHSU PCPs not exposed to the intervention.

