**Table 1**

Data Class	Examples include, but are not limited to:	Data source
Clinician characteristics	sex, age, degree (MD, DO, NP, PA, resident), years of practice	Public faculty data

Encounter information	Encounter date, encounter type, clinician ID, reason for visit, level of service, clinic ID, Department ID, encounter ICD9/10 problems, encounter CPT codes, encounter payor(s), skin cancer screening performed, use of skin cancer screening tool, use of SKLIP , biopsy performed, referral to dermatology, econsult to dermatology. Use of skin cancer dot phrase, Established vs. new patient.  Patient characteristics age, sex, race, ethnicity.	EHR, chart review
biopsy info/ pathology	Biopsy result, number of biopsies performed, number of skin lesions biopsies, Breslow thickness	EHR, chart review
Clinician knowledge and confidence	MTED pre- and post-evaluations,	From IRB approved Surveys ( IRB #19372 – “Educational Program for the Early Detection of Melanoma in Oregon” ).
practice pattern, referral practice	qualitative Interviews	Coded qualitative interview transcripts

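### The SAP's clinical outcomes are volumes of e-consults, referrals and biopsies, which cannot by themselves show better identification or triage of skin cancer

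*SAP*

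**What the plan says.** Protocol section 2 (Objectives) sets the question: whether the training "improves the ability of Primary Care Providers (PCPs) to identify and triage skin cancer". Section 4 (Study Design) adds the hypothesis that more skin cancers will be diagnosed, and at earlier stages. It lists among the primary endpoints "number of melanomas biopsied, mean and median Breslow depth of melanomas biopsied, number of other malignant skin tumors biopsied", followed by "total number of referrals to dermatology, number of referrals to dermatology for concerning moles". Table 1 in section 6 plans to collect "Biopsy result, number of biopsies performed, number of skin lesions biopsies, Breslow thickness", from the EHR and chart review.

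The SAP (Analyses) is one paragraph headed as the final approach. It reports descriptively the "rates of e-consults, dermatology referrals and biopsies performed (defined as the number of cases per 1000 patients". It fits a Poisson GEE with "an exchangeable correlation structure to compare referral outcomes", with training exposure, period and their interaction as predictors. Its one other outcome analysis is of test scores: "We conducted a paired t-test to evaluate change in knowledge scores". The SAP does not mention melanoma counts, other malignant counts, Breslow depth or concerning-mole referrals. It does not itemise what its referral outcomes are.

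**The concern.** Ability to identify and triage is a matter of discrimination: whether the lesions acted on are more often the ones that matter. A rate of biopsies, referrals or e-consults per 1000 patients does not carry that information, and neither document says which direction of change would count as better. The training in section 6 covers recognition, dermoscopy and triage. Better recognition can push referrals and biopsies up, and better dermoscopy and triage can bring unneeded ones down. A lower threshold for action also pushes them up.

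A training-by-period effect on referrals, of either sign, is therefore compatible with better or worse triage. A null result could conceal referrals that are better targeted. If such a result were taken as the answer to section 2, the conclusion would go beyond the data.

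**Working it through.** The documents state no malignant yield, effect size or power, so there is no figure of the plan's to reproduce. The check asks whether the SAP's biopsy rate can separate scenarios that differ in discrimination.

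**Inputs from the protocol**
- Biopsied individuals: up to 200 per clinic-year (section 5a), so 2 × 200 = 400. This is a ceiling and counts people. I treat it as one biopsy per person.
- Patients per year, from the totals in Tables 2 and 3: rural 6251 + 4737 = 10,988; urban 6670 + 5012 = 11,682; together 22,670.

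**Assumptions, not in the documents**
- Baseline malignant share 25% (range 15% to 40%).
- Biopsies rise 30%, to 400 × 1.30 = 520.

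**Step 1: the SAP's measure.** Before: 400 / 22,670 × 1000 = 17.6 per 1000. After: 520 / 22,670 × 1000 = 22.9 per 1000. The rate ratio is 1.30.

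**Step 2: yield behind the same rate.** Baseline malignancies are 0.25 × 400 = 100, a yield of 25.0%, or 4.0 biopsies per malignancy. The 120 extra biopsies may be:

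| Extra 120 biopsies | Malignancies after | Yield after | Biopsies per malignancy | SAP rate after |
|---|---|---|---|---|
| All benign | 100 | 100/520 = 19.2% | 5.2 | 22.9 |
| Same yield (25%) | 130 | 130/520 = 25.0% | 4.0 | 22.9 |
| 1.5 times the yield (37.5%) | 100 + 45 = 145 | 145/520 = 27.9% | 3.6 | 22.9 |

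The last column does not move. With 15% malignant at baseline, the all-benign case takes yield from 15.0% to 60/520 = 11.5% (6.7 to 8.7 biopsies per malignancy). With 40%, it goes from 40.0% to 160/520 = 30.8% (2.5 to 3.25).

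**Step 3: a malignant count alone.** Rows one and two have malignancies of 100 and 130. The rise to 130 comes purely from more sampling at unchanged yield. A count without a biopsy denominator therefore does not isolate discrimination either.

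**Step 4: how precisely yield could be estimated.** Pooling both arms, 100/400 against 100/520 gives z = 2.10, p = 0.035. That is not the relevant comparison, because the SAP's contrast is training by period. Assume half the baseline biopsies fall in each arm, with only the exposed arm changing: exposed 50/200 to 50/260, unexposed 50/200 in both periods.
- Interaction log odds ratio = ln[(50/210)/(50/150)] − 0 = ln(150/210) = −0.336.
- Variance = 4 × (1/50) + 3 × (1/150) + 1/210 = 0.0800 + 0.0200 + 0.0048 = 0.1048; SE = 0.324.
- z = 0.336 / 0.324 = 1.04, p = 0.30. The ratio of odds ratios is 0.71, with 95% interval exp(−0.336 ± 1.96 × 0.324) = 0.38 to 1.35.
- The same calculation gives p = 0.44 at 15% malignant and p = 0.15 at 40%.

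None of this allows for clustering by clinician or clinic, so real precision would probably be worse.

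**The case against.** The strongest reply is that section 4 calls this mainly a feasibility study of uptake and of changed screening behaviour. For that purpose, rates of e-consults, referrals and biopsies are legitimate outcomes. That stands: the rates should stay. It does not make them evidence for the objective in section 2 or for the earlier-detection hypothesis in section 4.

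Second, the plan is not made up only of volumes. Breslow depth is a primary endpoint and speaks to stage. "number of referrals to dermatology for concerning moles" is listed apart from total referrals and is closer to triage. The SAP does analyse knowledge. All true. But Breslow depth does not appear in the SAP, and concerning-mole referrals are still a count. The knowledge comparison is before against after among trainees, without controls, and it measures test performance rather than decisions on patients.

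Third, pathology may be incomplete. Sections 5 and 6 describe chart review for a subset of patients, because some biopsy results sit only in the chart. This is a fair caution about cost. It is largely answered because malignant tumours biopsied are already primary endpoints and Table 1 lists biopsy result and number of biopsies. Completeness still has to be shown.

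Fourth, biopsy yield says nothing about referrals, the only clinical outcome that is modelled. This stands: Table 1 names no diagnosis resulting from a referral. So does the point that the SAP is written in the past tense, so any added analysis is post hoc.

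A reader might also infer that the plan would declare success from a rise in referrals. The SAP attaches no such claim to them; the risk lies in later interpretation.

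**Conclusion.** The concern holds. The SAP's clinical outcomes are volumes, no outcome in either document relates malignancies to biopsies, and the same 17.6 to 22.9 per 1000 is compatible with yield falling to 19.2%, staying at 25.0% or rising to 27.9%. Those figures rest on the 400-person ceiling and on an assumed 25% malignant share and 30% rise. The conclusion that volume cannot separate the cases does not depend on them.

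Three stronger readings are not supported. Volumes need not rise equally under better detection and indiscriminate action: they can rise under either, by different amounts, and better triage may lower them. The protocol does not lack every measure of severity or ability, given Breslow depth and the knowledge tests. And yield would not settle the matter: the pooled p of 0.035 ignores the exposure comparison, and the interaction p is about 0.30 even if every extra biopsy is benign. The gap should be closed by descriptive reporting and limited wording, not by a new test of success.

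**What to change.** In the SAP and the results report:
- Using the biopsy results and biopsy numbers in Table 1, give malignancies per 1000 patients and malignant yield (malignant biopsies over all biopsies, and its inverse) by exposure group and period, with confidence intervals that allow for clustering. Show both, since malignancies can rise while yield falls.
- Label these analyses post hoc, and state by group and period the share of biopsies with a pathology result.
- Report the malignant counts and Breslow depth named in protocol section 4, or state why they are not analysed.
- Describe changes in referral, e-consult or biopsy volume alone as changed practice volume, not as improved identification or triage. State that referral appropriateness is not measured.
- Set no pass/fail rule on yield. No margin was specified in advance, and one chosen now would be post hoc.

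The cost is a derived variable and a table from data already planned, plus further chart review if pathology proves incomplete. The downside is wide intervals and a more cautious conclusion if only volume has changed.

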## 5) Study Population

### a) Number of Subjects

This study will be conducted at two primary care clinics. Within these two clinics, there are approximately 80 clinicians (e.g. MD, NP, PA, DO, APP).

We will invite all advanced practice providers (MD, NP, PA, DO) at these two clinic sites to participate in the multicomponent educational intervention, up to 40 clinicians per site. These clinicians will take part in the surveys imbedded in the Toolkit, surveys pre-and post-training, and live (in-person/virtual) trainings. Thus, we will recruit approximately 40 clinicians within the 2 clinics for the active intervention.

We will observe the in-person trainings and take detailed fieldnotes. We expect approximately 40 clinicians will participate in each training.

We will interview approximately 5-10 members per site within the clinic.

We will extract EHR data collected from patients from within these two clinics for the year prior and for 1-year post training implementation (2/1/2022-9/30/2024). We estimate up to 200 individuals with biopsies per year, per clinic. For a subset of patients, we will conduct a chart review to affirm use of specific devices to photograph lesions and biopsy results that are not readily ascertainable from EHR data alone.

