**8) Data Analysis**

Quantitative Data: Univariate descriptive statistics will be examined for all variables from the MTED pre- and post- evaluation survey. Comparison between data collection timepoints will be completed using Chi-square test (categorical), ANOVA (continuous), or Kruskal-Wallis one-way ANOVA test (continuous variables that are not normally distributed). Standard qualitative analysis techniques will be used for coding open-ended questions.

Descriptive statistics will be used to report screening, biopsy and referral characteristics at each data collection time points. Means, standard deviations will be reported for normally distributed continuous variables and medians and interquartile ranges (IQR) will be reported for non-

normally distributed ones. Frequencies and percentages will be calculated for categorical variables. The main comparison is between clinicians in the multicomponent educational intervention arm vs. clinicians at the same sites that do not have exposure to the multicomponent educational intervention. These two groups of clinicians are examined using a pre-post study design to evaluate outcomes including change in risk assessment, biopsy referral and identification of skin cancers. Linear mixed-effects regression models adjusting for clustering effects within study sites and other potential confounders will be used to compare the intervention and control arms in screening, biopsy and referral characteristics outcomes from baseline to post-intervention. A p-value < .05 will be considered statistically significant.

Qualitative data analysis: The study team will meet regularly to review fieldnotes and transcribed data and listen to and discuss key segments of the recorded interviews. Analyzing qualitative data as it is collected is crucial to monitoring data quality, refining interview guides, and monitoring theme saturation. This ongoing process will be used to track emerging themes and create a coding template to be used for more in-depth analysis. We will follow the 5-phase analysis strategy described by Miller and Crabtree (describing, organizing, connecting, corroborating/ legitimizing, representing). We will use an immersion-crystallization approach in which the team reads and discusses the data for each participant (immersion) to identify key findings (crystallization); first to identify key themes within each “case”, and then to identify cross-case findings.

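### The SAP post-dates the outcome window and departs from protocol section 8 without explanation, so the referral p-values cannot be read as prespecified tests

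*SAP*

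**What the plan says.** Protocol section 8 (Data Analysis) is the only forward-looking analysis plan in the documents. Its main comparison is trained against untrained clinicians at the same two sites, before and after the intervention. For screening, biopsy and referral outcomes it states: "Linear mixed-effects regression models adjusting for clustering effects within study sites and other potential confounders will be used". Its threshold is: "A p-value < .05 will be considered statistically significant".

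Protocol section 5a sets the EHR data period: "for the year prior and for 1-year post training implementation (2/1/2022-9/30/2024".

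The SAP is a single page dated 1 March 2025 and titled "Final approach to analysis". It is in the past tense, for example "We conducted a paired t-test to evaluate change in knowledge scores". It gives descriptive rates for e-consults, dermatology referrals and biopsies. For referral outcomes it reports a Poisson GEE with exchangeable correlation whose predictors are exposure, period and their interaction. It closes: "All analyses were two-sided, statistical significance was set at type I error of 5% and analyses were conducted using R Statistical Software".

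**The concern.** A p-value from a test at the 5% level has its usual meaning when the model, the adjustment set and the outcome were settled without sight of the results. Here the only text describing the GEE was written after the outcome window had closed and after the analyses had been run, and it differs from the plan that came before. A reader who sees a significance level and an SAP will naturally take the referral interaction as the planned test.

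The departures matter in themselves. Exposure was not randomised: the comparators are clinicians at the same two clinics who did not take the training, and they may differ in degree, experience, patient mix or prior interest in skin cancer. Section 8 answered this with confounder adjustment, and the SAP lists none. Section 8 also planned between-group models for three families of outcome, and the SAP names one for referrals alone. If the omitted analyses point elsewhere, the reader has no way to know.

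**Working it through.** **1. Timing.** From 30 September 2024 (protocol section 5a) to 1 March 2025 (SAP date): 31 + 30 + 31 + 31 + 28 + 1 = 152 days, or 152 / 30.44 = 5.0 months. If follow-up is instead taken as 12 months after the April–May 2023 initial training (to 31 May 2024), the gap is 9.0 months. Five months is therefore the cautious figure.

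**2. The two plans side by side.**

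| Element | Protocol section 8 | SAP | Same? |
|---|---|---|---|
| Significance level | 0.05, sidedness not stated | 5%, two-sided | Level yes; sidedness new |
| Contrast | Trained vs untrained, pre vs post | Exposure × period interaction | Yes |
| Model | Linear mixed-effects, clustering within sites | Poisson GEE, exchangeable correlation | No |
| Adjustment | Other potential confounders (not listed) | None among the listed predictors | No |
| Outcomes given a between-group model | Screening, biopsy, referral | Referral only; biopsy rates described, screening not mentioned | No |
| Date of, or reason for, the change | – | None given | – |

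Dermatology referrals are also named among the primary endpoints in protocol section 4, so referral was not introduced late as an outcome.

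**3. The stated level.** The SAP's two-sided 5% corresponds to |z| > 1.96 and equals the protocol's threshold. This reproduces the nominal level of one test and nothing more. Neither document gives a power calculation to check.

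**4. How large could selection be?** The documents do not say that more than one model was fitted. As an illustration only, suppose the section 8 model and the GEE were both fitted, each tested at two-sided 5%, and the result chosen after seeing both. With Z₁ and Z₂ bivariate normal with correlation ρ, the chance under the null that at least one rejects is

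1 − P(|Z₁| ≤ 1.96 and |Z₂| ≤ 1.96)

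| Assumed ρ | Chance of at least one rejection |
|---|---|
| 0.99 | 5.7% |
| 0.90 | 7.0% |
| 0.80 | 7.8% |
| 0 (independent) | 1 − 0.95² = 9.75% |

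Two models fitted to the same data and contrast should be strongly correlated, so the upper rows are the relevant ones. The calculation counts rejections in either direction. If the GEE was chosen without sight of results, the choice adds no inflation.

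**5. Can the two models be required to agree?** No. The linear model's interaction is a difference of differences. A Poisson model with the usual log link (the SAP does not name the link separately) gives a ratio of ratios. Take hypothetical rates of 10 rising to 15 in the exposed group and 4 rising to 7 in the unexposed:

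- additive: (15 − 10) − (7 − 4) = +2
- ratio: (15/10) / (7/4) = 1.50 / 1.75 = 0.86

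The signs differ, yet neither model is in error.

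**The case against.** The date and tense show when the SAP was written, not when the GEE was chosen. The investigators may have settled on a count model before opening the data, because referrals are counts; that would be a sensible reason and would carry no cost in error. This stands. A reader might infer that the model was picked because its result was favourable, but the documents contain no referral estimate, p-value or decision history, and do not support that.

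The 5% sentence can fairly be read as stating a nominal threshold that the protocol had already set, not as claiming control of error across analyses. This also stands. The level and the contrast were prespecified, and there is no ground for striking the level out.

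The section 8 model is a poor arbiter: it clusters on site with only two sites, and its confounders were never listed, so it cannot be reproduced exactly as planned. That limits it to a sensitivity role; it does not excuse leaving it out.

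Finally, protocol section 4 calls this mainly a feasibility pilot. That tempers any confirmatory reading, but the same section states effect hypotheses and primary endpoints, and both documents set a significance threshold. Labelling the p-values exploratory is consistent with a pilot.

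**Conclusion.** The point holds in a limited form. Prespecification of the GEE, of its unadjusted predictor list and of the restriction of between-group modelling to referrals is undocumented, and each departs from protocol section 8 without a stated reason. The referral p-values therefore cannot be read as prespecified tests.

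A reader might go further and conclude that the type I error is inflated by some definite amount. The documents do not allow that: the 5.7% to 7.8% range assumes that two models were fitted, that their correlation lies between 0.99 and 0.8, and that the result was picked after seeing both. A larger figure would need more candidate analyses than the documents show. Nor do the documents show that the referral conclusion is wrong or overstated, since no result is given.

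The conclusion rests on this being the only SAP. An earlier one, not among these documents, could settle the matter.

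**What to change.** 1. State in the SAP and the results record when and why the model, adjustment and modelled outcomes changed from section 8, and whether outcome data had been seen by then.
2. Unless earlier specification can be documented, label the GEE p-values nominal and exploratory. The 5% level can stay as the nominal threshold.
3. For each referral outcome, report the GEE interaction with its interval, both without and with adjustment for the clinician and patient covariates already collected (protocol Table 1: for clinicians sex, age, degree and years of practice; for patients age, sex, race and ethnicity). Place the section 8 linear mixed model beside it as a sensitivity analysis.
4. Report the same between-group contrast for the screening and biopsy outcomes that section 8 planned to model.
5. Do not make the conclusion depend on the two models agreeing, since one interaction is additive and the other a ratio. State the scale of each and discuss any difference.

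The cost is one extra table and a few sentences, using data already collected. The downside for the sponsor is that the referral claim may become less favourable.
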